5.3 Study Day Calculation

Study day is calculated relative to the date of Day 0 (randomization) and will appear in the listings where applicable. If the date of event is on or after Day 0, study day will be calculated as:

$$\text{Study day} = \text{date of event} - \text{date of Day 0 (randomization)}$$

5.4 Change from Baseline Calculation

Percent change from baseline to any time point will be calculated as follows:

$$[\text{Value (Post-baseline)} - \text{Value (Baseline)}] / \text{Value (Baseline)} \times 100$$

A negative value reflects a decrease in a given parameter, while a positive relative difference reflects an increase in the parameter.

5.5 Missing Data

For continuous endpoints, change from baseline will be set to missing at visits with missing values or where data were imputed to missing.

For binary endpoints, subjects with missing efficacy data or early withdrawals will be set to missing.

Additional rules for handling of missing data are detailed below:

- *Missing efficacy data.* Visits with missing data (due to a missed visit or missing component of a composite endpoint) will be set to missing.
- *Early withdrawals.* Visits following the early withdrawal will be set to missing.
- *Missing baseline value.* For efficacy endpoints, a missing value at baseline will not be imputed, and the endpoint will be set to missing for all visits.
- *Missing analytes/ retests.* If an analyte value is missing/ its concentration cannot be reliably determined (eg. sample was lost, damaged, etc.), a retest value will be used for that analyte. If an initial value is non-missing and reliable but the analyte was retested, the value that coincides with the date of clinical assessment will be used. If neither an initial and nor retest value are available, the analyte value will be set to missing.
- For missing dates, refer to **Section 5.8** of CLP-004.

5.5.1 Multiple Assessments and Visits

If a variable (e.g., MRI, TJC, SJC) has been assessed multiple times at the same visit, only the last assessment will be used.

Only completed scheduled visits will be included in summary tables (**Appendix B**). Listings will include scheduled and unscheduled visits (**Appendix C**).

5.6 Data Assurance

All tables, figures and data listings to be included in the report will be independently checked for consistency, integrity and in accordance with the study sponsor's SOPs.

5.7 Coding Dictionaries

AEs will be coded using the Medical Dictionary for Regulatory Activities (MedDRA, version 21.0 or later). Concomitant medications will be coded using the March 2019 or later version of the WHO Drug Global dictionary.

6 EXPLORATORY EFFICACY ANALYSES

6.1 General Considerations

For each follow-up time point, all dichotomous variables will be reported as responders / patients who have achieved that follow-up duration, percentage of responders, and 95% CI.

Values will be reported at each follow-up timepoint.

For continuous measures, mean, SD, median, minimum and maximum will be presented at each time point.

Time will be measured from initiation of stimulation. Therefore study participants originally randomized to stimulation will, for example, have Week 24 visits represented at 24 weeks of follow-up while study participants randomized to sham will have Week 24 visits represented as 12 weeks, since they will have been on stimulation on for 12 weeks at the Week 24 visit.

6.1.1 Missing endpoint data imputation

Below are the descriptions for the imputation methods that may be used throughout the efficacy analyses:

- *Observed case (OC)*. Missing values remain missing. For the categorical composite endpoints, in the case that some components are missing, the composite endpoint assessment will be derived based on the non-missing components. If non-missing components are not sufficient to determine final composite endpoint, then the composite endpoint will be set as missing. For continuous composite endpoints, if any components are missing, the composite endpoints will be set as missing.
- *Last observation carried forward (LOCF)*. Baseline and Day 0 measurements will not be carried forward to post-baseline. Only measurements post Day 0 will be LOCF for continuous and binary response measures. For the composite endpoints, the last non-missing, post-Day 0 observation will be carried forward to subsequent visits for each individual component first, and then the composite endpoints using individual components imputed by LOCF will be calculated as described above. If a subject does not have a non-missing observed record for a post-Day 0 visit, the last post-Day 0 record prior to the missed visit will be used. If the last non-missing observation prior to the missing visits cannot be determined due to multiple measurements occurring at the same time or the time not available within the same day, the worst outcome will be used for LOCF. If missing components still exist after LOCF, the composite endpoints will be calculated using the same rules as described in OC.
- *Non-responder imputation (NRI)*. For all binary response measurements, starting from OC, all missing will be set as non-responders.

If subject only had baseline measurements, LOCF and OC analyses will not include this subject. But this subject will be treated as non-responder in NRI analyses.

6.2 Clinical Variables

For descriptions and definitions of ACR components (TJC28, SJC28, Subject's Pain Assessment, SGA, EGA, HAQ-DI, hsCRP), refer to Section 8.2 of CLP-004.

6.2.1 ACR20/50/70

A subject achieves ACR20/50/70 response when this subject experiences a $\geq 20\%/50\%/70\%$, respectively improvement from baseline to a given timepoint in TJC28, SJC28, and at least 3 of the following 5 items:

- Subject's pain assessment
- SGA
- EGA
- HAQ-DI
- hsCRP

For all visits, if any of the component scores are missing, then those scores will be considered as not having met the criteria for improvement. If 3 or more of the 5 remaining ACR measures are missing, ACR20/50/70 will each be considered missing.

For component scores with missing baseline values or a baseline value of 0, the percentage improvement cannot be calculated, and the component will be considered as not having met the criteria for improvement for all visits.

20/50/70 response for each component (TJC28, SJC28, Subject's Pain Assessment, SGA, HAQ-DI, EGA, hsCRP) corresponds to 20, 50 and 70% improvement from baseline to a given timepoint, respectively.

6.2.2 DAS28-CRP

The Disease Activity Score (DAS) is a derived measurement of 4 components with differential weighting:

- TJC28
- SJC28
- hsCRP (mg/L)
- SGA

A total score ranges from 0 to 10 and is computed as follows:

$$\text{DAS28-CRP} = 0.56 * \text{sqrt}(\text{TJC28}) + 0.28 * \text{sqrt}(\text{SJC28}) + 0.36 * \text{ln}(\text{CRP}+1) + 0.014 * \text{SGA} + 0.96$$

If one of the components is missing at an individual assessment point, the DAS28-CRP value for that assessment will be set to missing. An alternative imputation method for missing components may be applied as described in Section **6.1.1**.

The DAS28-CRP score corresponds to the current RA activity:

- 0 to < 2.6 Remission
- 2.6 to < 3.2 Low disease activity (LDA)
- 3.2 to \leq 5.1 Moderate activity
- > 5.1 High activity

A DAS28-CRP score reduction by 1.2 represents the MCID.

6.2.3 DAS28-CRP Good/Moderate EULAR Response

DAS28-CRP good/moderate EULAR response is defined based on the combination of the current DAS28-CRP score and its improvement relative to baseline as illustrated in **Table 3**.

A subject is considered having a moderate treatment response if:

- DAS28-CRP score improvement from baseline to a given timepoint is > 0.6 and \leq 1.2, and the DAS28-CRP score at that timepoint is \leq 5.1; or
- DAS28-CRP score improvement from baseline to a given timepoint is > 1.2, and the DAS28-CRP score at that timepoint is > 3.2.

A subject is considered having a good treatment response if:

- DAS28-CRP score improvement from baseline to a given timepoint is > 1.2 and the DAS28-CRP score at that timepoint is \leq 3.2.

Table 3: EULAR Response Criteria

DAS28-CRP Score at a Given Timepoint	DAS28-CRP Score Decrease from Baseline Value to a Given Timepoint		
	> 1.2	> 0.6 to \leq 1.2	\leq 0.6
\leq 3.2	Good response	Moderate response	No response
> 3.2 to \leq 5.1	Moderate response	Moderate response	No response
> 5.1	Moderate response	No response	No response

If the post-baseline DAS28-CRP score is missing, then the corresponding EULAR category will be missing.

Missing DAS28-CRP values will be set as missing.

6.2.4 CDAI

The Clinical Disease Activity Index (CDAI) is a composite score consisting of the sum of:

- SJC28
- TJC28
- SGA/10
- EGA/10

The CDAI score is calculated as follows and ranges from 0 to 76 with higher values representing higher disease activity:

$$\text{CDAI} = \text{TJC28} + \text{SJC28} + \text{SGA} + \text{EGA}$$

The CDAI score corresponds to the current RA activity:

- 0 to ≤ 2.8 Remission
- >2.8 to ≤ 10 Low disease activity (LDA)
- >10 to ≤ 22 Moderate activity
- > 22 High activity

The MCID varies depending on RA activity at baseline:

- -12 for high activity
- -6 for moderate activity
- 1 for low activity

If one of the components is missing at a given assessment point, no imputations will be done, and the CDAI value for that assessment will be set to missing. An alternative imputation method for missing components may be applied as described in Section 6.1.1.

6.2.5 RAMRIS

RAMRIS is the standardized system for RA MRI scoring of 4 different types of joint pathologies in the wrist and the hand. A total score for each pathology is generated by the summation of individual joint/bone scores as follows:

- *Synovitis*. 8 joints each scored on a scale from 0 = normal to 3 = severe, resulting in a total score from 0 to 24.
- *Bone erosion*. 25 bones each scored on a scale from 0 to 10, resulting in a total score from 0 to 250. An increase of > 0.5 from baseline to Week 12 will represent disease progression.
- *Osteitis*. 25 bones scored on a scale from 0 to 3, resulting in a total score from 0 to 75.

- *CARLOS (cartilage loss)*. 25 joints each scored on a scale from 0 to 4, resulting in a total score from 0 to 100.

Subjects will undergo MRI at Week 24, and the MRI images will be scored by the same independent centralized blinded readers who scored baseline and Week 12 MRIs. Scores for each bone/joint will be calculated as the average of the score provided by each of the two readers. If a RAMRIS score from one of the readers is missing, then the RAMRIS score from the other reader will be used. If the score was missing for both readers at any given time point, the average score is considered missing. An imputation method for missing components may be applied as described in Section 6.1.1.

The smallest detectable change (SDC) will be calculated for each of the joint pathologies to assess whether a patient experienced a change beyond measurement error. The SDC is calculated as:

$$\pm 1.96 \times \text{SD}_{\Delta(\text{CHANGE SCORES})} / (\sqrt{2} \times \sqrt{k})$$

where CHANGE SCORE = change in RAMRIS total score between two timepoints, $\text{SD}_{\Delta(\text{CHANGESCORES})}$ represents the standard deviation of difference in change scores between the two readers, and k= the number of readers (Bruynesteyn et al., 2005).

In addition, subgroup analyses will be performed for subjects with and without baseline joint damage that is predictive of future progression (Gandjbakhch et al, 2014).

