May not be reproduced outside of SetPoint Medical without written permission from Document Control.

46 of 111

	
baseline to Week 12, 24, 48, 96, 144 and 192
 
 RAMRIS bone erosion, osteitis, synovitis, and CARLOS score change from baseline to Week 12 and 24 RAMRIS bone erosion progression (> 0.5) rate from baseline to Week 12 and 24 Change in plasma biomarker concentrations (e.g., IL-6, SAA, MMP3) 	
Safety		
To evaluate the safety of the SetPoint System	
Incidence of AEs and SAEs from informed consent to Week 264
 
Incidence of device malfunctions from Implant Procedure to Week 264
	
The incidence of treatment emergent AEs and SAEs that are more common in the treatment group compared to control is a standard measure of the safety. The incidence of device malfunction informs about the device reliability.

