4.2 Exploratory Analysis

During the open-label follow-up, changes in exploratory efficacy endpoints at Week 24, 48, 96, 144 and 264 (end of study) will be evaluated in comparison to baseline and Day 0 for the treatment population and Week 12 for the crossover population using data for all subjects available at a given timepoint (**Table 2**). Refer to Section 5.2 for definitions of populations.

Table 2: Summary of Exploratory Efficacy Endpoints

Endpoint	Display	TOL	COL	Subgroup
ACR20/50/70 response	T, L	Y	Y	Y [1]
DAS28-CRP moderate/good EULAR response	T, L	Y	Y	Y
DAS28-CRP response (MCID)	T, L	Y	Y	Y
HAQ-DI score change and response (MCID)	T, L	Y	Y	Y
ACR components (TJC28, SJC28, Subject Pain, SGA, HAQ-DI, EGA, hsCRP) 20/50/70response	T, L	Y	Y	--
DAS28-CRP score change, LDA/remission	T, L	Y	Y	--
CDAI score change, LDA/remission, response (MCID)	T, L	Y	Y	--
RAMRIS (bone erosion, osteitis, synovitis, CARLOS) score change, progression (bone erosion) at Week 24	T, L	Y	Y	--
EQ-5D-5L score change	T, L	Y	Y	--
SF-36/PCS/MCS score change	T, L	Y	Y	--
Percent change in inflammatory biomarkers at Week 24	T, L	Y	Y	--
Subject satisfaction at Week 24	T, L	Y	Y	--

Abbreviations: ACR, American College of Rheumatology; CARLOS, cartilage loss score; CDAI, Clinical Disease Activity Index; COL, control to open label; CRP, C-reactive protein; DAS, Disease Activity Score; EGA, evaluator's global assessment; EQ-5d-5L, EuroQol 5 domains 5 levels; EULAR, European League Against Rheumatism; HAQ-DI, Health Assessment Questionnaire Disability Index; hsCRP, high sensitivity CRP; L, listings; LDA, low disease activity; RAMRIS, Rheumatoid Arthritis MRI Scoring System; SF-36, Short Form Survey with 36 items; SGA, subject's global assessment; T, tables; TJC, tender joint count; TOL, treatment to open label; SJC, swollen joint count; Y, yes.

[1] Subgroup analyses as defined in Section 6.3

Note: All score values are determined at all timepoints, unless stated otherwise. All response rates are determined based on change from baseline (i.e., on the day of informed consent for OL PTE population and Week 12 for CO PTE population) to a specified timepoint. Refer to Section 5.2 for definitions of populations Sections 6.2 for definition of response for specific endpoints.

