Progression rate from baseline (> 0.5)		
N [3]	xx (xx.x%)	xx (xx.x%)
Mean (SD)	xxx.x (xxx.xx)	xxx.x (xxx.xx)
Median	xxx.xx	xxx.xx
Min-Max	xxx.x – xxx.x	xxx.x – xxx.x
RAMRIS osteitis score		
Baseline [4]		
N [3]	xx (xx.x%)	xx (xx.x%)
Mean (SD)	xxx.x (xxx.xx)	xxx.x (xxx.xx)
Median	xxx.xx	xxx.xx
Min-Max	xxx.x – xxx.x	xxx.x – xxx.x
Week 24		
N [3]	xx (xx.x%)	xx (xx.x%)
Mean (SD)	xxx.x (xxx.xx)	xxx.x (xxx.xx)
Median	xxx.xx	xxx.xx
Min-Max	xxx.x – xxx.x	xxx.x – xxx.x
Change from baseline [4] (SDC: x.xx)		
N [3]	xx (xx.x%)	xx (xx.x%)
Mean (SD)	xxx.x (xxx.xx)	xxx.x (xxx.xx)
Median	xxx.xx	xxx.xx

Variable	TOL [1] (N=xxx)	COL [2] (N=xxx)
Min-Max	xxx.x – xxx.x	xxx.x – xxx.x
95% CI	(xx.x, xx.x)	(xx.x, xx.x)
RAMRIS CARLOS score		
Baseline [4]		
N [3]	xx (xx.x%)	xx (xx.x%)
Mean (SD)	xxx.x (xxx.xx)	xxx.x (xxx.xx)
Median	xxx.xx	xxx.xx
Min-Max	xxx.x – xxx.x	xxx.x – xxx.x
Week 24		
N [3]	xx (xx.x%)	xx (xx.x%)
Mean (SD)	xxx.x (xxx.xx)	xxx.x (xxx.xx)
Median	xxx.xx	xxx.xx
Min-Max	xxx.x – xxx.x	xxx.x – xxx.x
Change from baseline [4] (SDC: x.xx)		
N [3]	xx (xx.x%)	xx (xx.x%)
Mean (SD)	xxx.x (xxx.xx)	xxx.x (xxx.xx)
Median	xxx.xx	xxx.xx
Min-Max	xxx.x – xxx.x	xxx.x – xxx.x
95% CI	(xx.x, xx.x)	(xx.x, xx.x)

Abbreviations: CARLOS, cartilage loss score; CI, confidence interval; COL, Control to Open Label; RAMRIS, Rheumatoid Arthritis MRI Scoring System; SDC, Smallest Detectable Change; TOL, Treatment to Open Label

- [1] Treatment to Open Label (TOL): The TOL population comprises treatment subjects from ITT population who received active stimulation through Week 12, completed Week 12 assessments, continued to receive active stimulation during open-label follow-up, and for whom follow-up data are available.
- [2] Control to Open Label (COL): The COL population comprises control subjects from ITT population who received non-active (sham) stimulation through Week 12, switched to active stimulation after completing Week 12 assessments, continued to receive active stimulation during open-label follow-up, and for whom follow-up data are available.
- [3] Percentage calculated based on each analysis population (i.e., TOL, COL)
- [4] Baseline on the day of informed consent for TOL and Week 12 for COL
- [5] Initiation of stimulation at Day 0 for TOL and Week 12 for COL

Reference: Listing 16.x.x.x

SOURCE: xxxxx SAS 9.4 {program location} {run date/time} }

Table 14.8.2.14
 EQ-5D-5L

Variable	TOL [1] (N=xxx)	COL[2] (N=xxx)
EQ-5D-5L Index score		
Baseline [4]		
N [3]	xx (xx.x%)	xx (xx.x%)

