Note to programmer: Baseline on the day of informed consent for TOL and at Week 12 for COL

SOURCE: xxxxx SAS 9.4 {program location} {run date/time}

Listing 16.8.2.7.8
RAMRIS

Population Analysis	Subject ID	Visit	Synovitis Score	Osteitis score	Bone Erosion score	Progression? (Bone Erosion Increase > 0.5)	CARLOS
TOL	xx-xxxx	Baseline (Screening) Week 24 % Change from baseline	xx	xx	xx	— — N	xx
COL	xx-xxxx	Baseline (Week 12) Week 24 Change from baseline					

Note to programmer: Baseline during Screening for TOL and at Week 12 for COL

SOURCE: xxxxx SAS 9.4 {program location} {run date/time}

Listing 16.8.2.7.9
EQ-5D-5L

Population Analysis	Subject ID	Visit	Mobility	Self-Care	Usual Activities	Pain/Discomfort	Anxiety/Depression	EQ-VAS	Index value
TOL									
	xx-xxxx	Week 24	x	x	x	x	x	xxx	xx
		Week 48							
		Week 96							
		Week 144							
COL									
	xx-xxxx	Week 24	x	x	x	x	x	xxx	xx
		Week 48							
		Week 96							
		Week 144							
		Week 192							

SOURCE: xxxxx SAS 9.4 {program location} {run date/time}

Listing 16.8.2.7.10
SF-36

Population Analysis	Subject ID	Visit	PCS score	MCS score
TOL				
	XX-XXXX	Week 24		
		Week 48		
		Week 96		
		Week 144		
COL				
	XX-XXXX	Week 24		
		Week 48		
		Week 96		
		Week 144		
		Week 192		

SOURCE: xxxxx SAS 9.4 {program location} {run date/time}

Listing 16.8.2.7.11
Subject Satisfaction

Population Analysis	Subject ID	Visit	How satisfied are you with the SetPoint System for treatment of your RA	Would you recommend it to a family member or a friend?	Comment
TOL	xx-xxxx	Week 24	Very satisfied	Yes	
	xx-xxxx	Week 24	Satisfied	Yes	
	xx-xxxx	Week 24	Neither satisfied nor dissatisfied	No	
	xx-xxxx	Week 24	Somewhat dissatisfied	No	
	xx-xxxx	Week 24	Very dissatisfied	No	
COL	xx-xxxx	Week 24	Very satisfied	Yes	
	xx-xxxx	Week 24	Satisfied	Yes	
	xx-xxxx	Week 24	Neither satisfied nor dissatisfied	No	
	xx-xxxx	Week 24	Somewhat dissatisfied	No	
	xx-xxxx	Week 24	Very dissatisfied	No	

SOURCE: xxxxx SAS 9.4 {program location} {run date/time}

Listing 16.8.2.7.12
Inflammatory Biomarkers

Population Analysis	Subject ID	Visit	IL-6 (pg/mL)	IL-6 % Change	SAA (μg/mL)	SAA % Change	MMP-3 (pg/mL)	MMP-3 % Change
TOL		Baseline		--		--		--
	XX-XXXX	Day 0						
		Week 12						
		Week 24						
		Week 36						
		Week 48						
		Week 60						
		Week 72						
		Week 84						
		Week 96						
		Week 108						
		Week 120						
		Week 132						
		Week 144						
		Week 156						
		Week 168						
		Week 180						
		Week 192						

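### The long-term SAP defines erosion progression by the wrong visit for its Week 24 MRI analysis, and its RAMRIS table shell omits synovitis and treats a yes/no rate as continuous

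*SAP*

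**What the plan says.** The SAP has two parts. CLP-004 covers the blinded period to Week 12, and CLP-008 covers the open-label follow-up. Section 6.2.5 of CLP-008 concerns the Week 24 scan: "Subjects will undergo MRI at Week 24, and the MRI images will be scored by the same independent centralized blinded readers". The same section defines erosion progression thus: "An increase of > 0.5 from baseline to Week 12 will represent disease progression". CLP-004 Section 8.6.1 has the identical sentence, which is right there because that plan stops at Week 12.

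Table 2 in CLP-008 Section 4.2 plans "RAMRIS (bone erosion, osteitis, synovitis, CARLOS) score change, progression (bone erosion) at Week 24". Protocol Table 3 (Section 8) plans "RAMRIS bone erosion progression (> 0.5) rate from baseline to Week 12 and 24". The note to Table 2 sets the reference for response rates as "on the day of informed consent for OL PTE population and Week 12 for CO PTE population" (former names for TOL and COL) and sends the reader to Section 6.2 for the response definitions. Footnote 4 of Table 14.8.2.13 agrees: "Baseline on the day of informed consent for TOL and Week 12 for COL". The note under Listing 16.8.2.7.8 reads "Baseline during Screening for TOL and at Week 12 for COL".

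The shell of Table 14.8.2.13 has blocks for erosion, osteitis and CARLOS. Its progression row calls for N, mean, SD, median and range. CLP-008 Section 6.1 requires every dichotomous variable to be reported as a count of responders over subjects at that time point, with a percentage and a 95% CI.

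**The concern.** Section 6.2.5 is the operative definition. Table 2 names the right visit but defers to Section 6.2 for the rule, so a programmer who follows the cross-reference arrives at the sentence that says Week 12. The neighbouring definitions of ACR and EULAR response in CLP-008 were generalised to any time point; the RAMRIS definition was not.

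By the protocol's schedule of assessments, Week 24 is the only MRI after control subjects cross over to active stimulation, so no later scan can stand in for it. A COL progression rate of 0% that came from the definition could be misread as erosion halting once stimulation began. A synovitis block missing from the shell could mean that a planned summary is never produced.

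**Working it through.** No power or alpha figure is involved. The check compares definitions and puts them into one formula.

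**1. The progression rule.** Let E(v) be the erosion total at visit v. The rule in 6.2.5 is E(Week 12) − E(baseline) > 0.5.

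| Population and reading of baseline | Change under 6.2.5 as written | Uses Week 24 scan? | Change if 6.2.5 named Week 24 |
|---|---|---|---|
| TOL, Screening | E(Week 12) − E(Screening) | No | E(Week 24) − E(Screening) |
| COL, Week 12 (Table 2 note, table footnote, listing) | E(Week 12) − E(Week 12) = 0, and 0 > 0.5 is never true: rate 0% | No | E(Week 24) − E(Week 12) |
| COL, Screening (6.2.5 mentions baseline and Week 12 scans as separate scans) | E(Week 12) − E(Screening): the sham-period change, not necessarily 0 | No | Not the reference stated elsewhere |

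The Week 24 scan is unused on every reading. The COL rate is fixed at 0% on only one of the two.

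**2. Which visit was intended.** Protocol Table 3 gives Weeks 12 and 24. CLP-008 Table 2 gives Week 24. The table shell puts the progression row after the Week 24 change rows. The listing runs from reference scan to Week 24 to change, with a progression flag not limited to Week 12. The sentence in 6.2.5 stands alone against these four.

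**3. The table shell.** Table 2 plans four scores: erosion, osteitis, synovitis and CARLOS. The shell has three, so 4 − 3 = 1 is missing. The matching CLP-004 shell (Table 14.1.2.13) has a synovitis block and reports progression as a count and percentage with a CI, so both departures are specific to CLP-008.

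**4. Comparability after correction.** From the schedule of assessments, Week 12 is Day 84 and Week 24 is Day 168. The COL interval is 168 − 84 = 84 days. For TOL, the Screening scan falls between consent and implant (at most 30 days apart), and implant precedes Day 0 by 14 to 21 days. The TOL interval therefore runs from 0 + 14 + 168 = 182 days to 30 + 21 + 168 = 219 days. Leaving visit windows aside, TOL subjects have about 182/84 = 2.2 to 219/84 = 2.6 times as long in which to pass the same 0.5 threshold.

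**The case against.** The best defence is that the intent is plain. Table 2, the table shell, the listing and the protocol all point to Week 24, and the sentence in 6.2.5 is evidently carried over from CLP-004. An attentive programmer would query it. Even if the flag were wrong, the same table prints the COL erosion change from Week 12 to Week 24 with its range and CI, and the listing shows each subject's scores, so a 0% rate beside individual increases above 0.5 would look wrong. Synovitis is still committed to in Table 2 for both a table and a listing, defined in 6.2.5 and listed by subject. Section 6.1 already governs the format of binary results. All of this is exploratory and descriptive.

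Most of that stands, and it limits the point to an internal contradiction plus shell errors. It does not remove the contradiction, because the text that names Week 24 hands the definition to the text that names Week 12.

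Three stronger readings are tempting but not supported:

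- A reader might infer that the Week 24 imaging results as a whole would be wrong or absent. The shell correctly specifies the Week 24 scores and changes for erosion, osteitis and CARLOS in both populations.
- A reader might infer that COL progression is 0% with certainty. That requires literal programming together with the Week 12 baseline; the Screening reading gives a different figure, also wrong.
- A reader might infer that the scans of all 250 or so randomised subjects are lost, or that TOL would exactly repeat the published Week 12 rate. The scans still feed the score changes, and TOL and COL are subsets of the ITT population that CLP-004 analyses.

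**Conclusion.** The point holds in limited form. Section 6.2.5 names the wrong visit for the one binary MRI endpoint that CLP-008 reports, and contradicts Table 2, the listing and the protocol. Followed literally, it yields no Week 24 progression rate for either population. Two errors in the Table 14.8.2.13 shell stand however 6.2.5 is read: one of four planned scores has no block, and a rate is summarised with continuous statistics against Section 6.1.

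The effect is confined to the exploratory progression flag and the synovitis summary table. The primary and key secondary conclusions are untouched. The numerical consequence for the flag depends on literal programming and, for COL, on which scan is taken as baseline. It is worth correcting because the Week 24 scan is the only post-crossover MRI and the correction costs almost nothing.

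**What to change.** - In CLP-008 Section 6.2.5, define progression as an increase of more than 0.5 from the population's stated reference scan (Screening for TOL, Week 12 for COL) to Week 24. Name the TOL reference as Screening in footnote 4 of Table 14.8.2.13 as well: Protocol Section 11.2.2 lets the MRI follow the day of consent.
- Add a synovitis block to Table 14.8.2.13: scores, change with smallest detectable change, and 95% CI.
- Under progression, replace the mean, SD, median and range rows with n (%) and a 95% CI.
- State beside the progression rates that the TOL and COL intervals differ and the two rates are not directly comparable.
- While editing, make the change row of Listing 16.8.2.7.8 consistent; it is a percentage for TOL and a plain change for COL.

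The cost is a phrase in the text, one table shell, a footnote and a listing label, before programming. No new data or assessments are needed.
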